10.5 Appendix 5: Participant Assessments

Categorical Pain Intensity Scale (predose)

Finish the statement: "M	y pain at this time is" by checking the appropriate box.
	□ No Pain (0)
	☐ Mild Pain (1)
	☐ Moderate Pain (2)
	☐ Severe Pain (3)

Numerical Rating Scale (pre-dose and post-dose)

Circle a number to indicate level of pain (from 0 to 10) below to indicate the severity of the pain you are experiencing at this time.

No pain	0 1	2	3	4	5	6	7	8	9	10	Worst possible pain	
------------	-----	---	---	---	---	---	---	---	---	----	---------------------------	--

Categorical Pain Relief Rating Scale (post-dose)

Finish the statement: " My relief from my starting pain is"" by checking the appropriate box.

No Relief (0)
A Little Relief (1)
Some Relief (2)
A Lot of Relief (3)
Complete Relief (4)

Page 64 of 67

Global Assessment of Pain (post-dose)

Finish the statement: " What is your overall rating of the study medication you received?"
by checking the appropriate box.

Ш	Poor (0)
	Fair (1)
	Good (2)
	Very Good (3)
	Excellent (4)

Version 4.0 / 13 Mar 2023

Page 65 of 67

10.6 Appendix 6: Abbreviations

AE Adverse Event

ANCOVA Analysis of Covariance

CDER Center for Drug Evaluation and Research

CDISC Clinical Data Interchange Standards Consortium

CI Confidence Interval COX Cyclooxygenase

CRO Clinical Research Organization

CSR Clinical Study Report

(e)CRF (electronic) Case Report Form

EOT End of Trial

FDA Food and Drug Administration

GCP Good Clinical Practice

GMP Good Manufacturing Practice

IB Investigator Brochure
ICF Informed Consent Form

ICH International Conference on Harmonization

IRB/IEC Institutional Review Board/Independent Ethics Committee

ITT Intent-to-Treat

MedDRA Medical Dictionary for Regulatory Activities

NPO nil per os

NRS Numerical Rating Scale

NSAID Nonsteroidal Anti-inflammatory Drug

OTC Over-the-Counter

PID Pain Intensity Differences

PP Per Protocol

QA Quality Assurance

RNR Randomization Number

SAE Serious Adverse Event

SAP Statistical Analysis Plan

SAS Statistical Analysis Software

SNR Screening Number

SSRI Selective Serotonin Uptake Inhibitors

SoA Schedule of Activities SOC System Organ Class

SPID Summed Pain Intensity Difference SUSAR Serious Unexpected Adverse Reaction TEAE Treatment-Emergent Adverse Event

TOTPAR Total Pain Relief

UI Unique Identification (formulation)

Page 66 of 67

11. References

Moderate caffeine consumption during pregnancy. Committee Opinion No. 462. American College of Obstetricians and Gynecologists. Obstet Gynecol 2010;**116**: 467–8.

Capone, M. L., S. Tacconelli, M. G. Sciulli, M. Grana, E. Ricciotti, P. Minuz, P. Di Gregorio, G. Merciaro, C. Patrono and P. Patrignani (2004). "Clinical pharmacology of platelet, monocyte, and vascular cyclooxygenase inhibition by naproxen and low-dose aspirin in healthy subjects." Circulation **109**(12): 1468-1471.

Cooper, S. A. and W. T. Beaver (1976). "A model to evaluate mild analgesics in oral surgery outpatients." Clin Pharmacol Ther **20**(2): 241-250.

1 INTRODUCTION

This is a single center, randomized, double-blind, parallel, placebo-controlled study in participants experiencing moderate to severe postoperative dental pain.

This proposed product is intended to be a tablet with a fixed dose combination of 220 mg naproxen sodium and 65 mg caffeine based on the recently completed dose ranging study. The purpose of this product is to provide temporary relief of minor aches and pains due to minor pain of arthritis, muscular aches, backache, menstrual cramps, headache, and toothache for adults and children over 12 years of age.

This pivotal efficacy study is intended to examine the analgesic effect of this FDC compared to its components, naproxen sodium and caffeine to satisfy the combination rule set forth in 21CFR 330.10(a)(4)(iv).

This Statistical Analysis Plan (SAP) describes the statistical methods and data handling procedures to be followed during the final reporting and analyses of data collected for the study Protocol 22093.

This SAP should be read in conjunction with the study protocol and case report form (CRF). This version of the plan has been developed using the protocol Version 4.0, dated MAR 13, 2023 and CRF Version 5.0, dated APR 14, 2023.

The table of contents and templates for the Tables, Figures and Listings (TFLs) will be produced in a separate document. Any deviations from this SAP will be described and justified in the Clinical Study Report (CSR).

The preparation of this SAP has been based on International Conference on Harmonization (ICH) E9.

2 STUDY DETAILS

2.1 Study Objectives

The primary objective of the study is:

1. To compare a single oral dose of the FDC relative to naproxen sodium 220mg, Caffeine 100 mg and placebo.

The secondary objectives of the study are:

- 2. To compare a single oral dose of the FDC relative to naproxen sodium 220mg, caffeine 100 mg and placebo. The assessments are made in terms of:
 - Pain intensity differences
 - Measures of pain relief
 - Duration of analgesic efficacy

- Onset of pain relief as determined by the time of perceptible relief
- Onset of pain relief as determined by the time to meaningful relief
- Overall relief from pain based on measures of pain intensity and pain relief
- Global assessment of the investigational product
- 3. To assess the safety and tolerability of the investigational product in terms of adverse events (AEs) and clinical parameters.

2.2 Study Design

This is a single center, randomized, double-blind, parallel, placebo-controlled study in participants experiencing moderate to severe postoperative dental pain. The study will consist of a Prescreening telephone call, a Screening Visit, a one day Treatment Period and a Post-Operative phone call or visit. Eligible participants who have undergone surgical extraction of three or four third molars, 2 of which were mandibular partial or full bony impacted third molars will be kept in-house and evaluated for efficacy and safety at the study site through completion of all trial procedures.

Qualified participants will then be randomized into one of five treatments. Approximately 750 participants will be screened prior to surgery. Approximately 540 will have surgery and approximately 528 will be randomized to a specific treatment. For an overview on the study design and study procedures, see figure 1 below:

-	Screening Phase		Treatm		Follow up Phase		
Trial Days	Day -28 to -1	Day 1 Pre-surgery	Day 1 Surgery	Day 1 Post-surgery	Day 1	Day 2	2-5 days after discharge
		Check-in to study site	Surgical teeth extraction	Categorical pain NRS pain	Stopwatch method NRS pain, Pain relief	Stopwatch method NRS pain Pain relief Global assessment	Phone call or visit

Figure 1 – Design Overview

★ = randomized study intervention of:

naproxen sodium/caffeine 220/65 mg; naproxen sodium/caffeine 2 x 220/65 mg; naproxen sodium 220 mg; caffeine 100 mg; or placebo.

Screening Phase

Eligible participants will be screened and selected up to 28 days prior to oral surgery and dosing with investigational product (study intervention).

Treatment Phase

Following selection, qualified participants will enter the Treatment Phase and be scheduled for their surgical teeth extractions. After completion of the surgical teeth extractions, participants will remain at the study site for observation. Participants with appropriate pain requirement will be randomized into one of five (5) treatment groups receiving study intervention. Participants will rate their pain severity and pain relief over the next 24 hours. Onset of analgesia will be measured using a two-stopwatch approach. The first stopwatch will be used to capture the time when any pain relief is first perceived. The second stopwatch will be used to capture the time when pain relief becomes meaningful to the participant. After completion of all trial procedures, participants will be discharged from the study site.

All participants are required to remain at the study center and complete all relevant assessments regardless of rescue.

Follow-Up Phase

Participants will be evaluated at a post-operative visit/call approximately 2-5 days after discharge for follow up for any adverse events or medications not known at the time of treatment.

The duration of each participant's participation will be approximately 37 days. See study schedule of assessment, table 1 below:

Table 1: Schedule of Assessment

Protocol Activities	Screening Visit	Dosing Inpa	Period tient	End of Trial Call or Visit
	(within 28 days prior to oral surgery)	Day 1	Day 2	(2-5 days after discharge)
Written Informed Consent	x			
Inclusion/Exclusion Reviewed	x	х		
Medical/Medication History (incl. caffeine consumption)	х	x		
Physical and Oral Examination	х			
Vital Signs ^a	x	x	x	
Urine for Drug Screen	x	x		
Breath or saliva alcohol test	x	x		
Dental x-ray examination	x			
Urine Pregnancy Test (if applicable)	x	x		
Admission to Unit		x		
Oral surgery (between 0530 h and 1030 h)		x		
Randomization Number Assigned		x		
Investigational Product Administration		x		
Surgical Trauma Rating		x		
Stop watch method (perceptible and meaningful relief)		x	x	
Categorical Pain Rating Scale ^b		x	x	
Pain Intensity Numerical Rating Scale (NRS) °		x	x	
Categorical Pain Relief Rating Scale °		x	x	
Global Assessment of Pain Relief ^d			x	
Concomitant Medications		х	x	x
Adverse Events Assessed	x	x	x	x
Discharge from Unit the afternoon/evening of Day 2			x	

^a vital signs (blood pressure, pulse rate, and respiration after sitting for at least 5 minutes). On Day 1, vital signs are due pre-operatively, post-surgery at 1 hour, 12 hours and on Day 2, 24 hours (-30 minutes pre-surgery; +30 minutes post-surgery; +/- 30 minutes from hours 1 through 24) after study medication dosing

^b to be completed prior to dosing

^c Pain Intensity NRS to be completed at baseline (predose), and Pain Intensity NRS and Categorical Pain Relief will be assessed 0.5, 1, 1.5, 2, 3, 4, 5, 6, 7, 8, 9, 10, 11, 12, 14, (16, 18, 20 if awake), 22 and 24 hours (+/-5 minutes over the first 8 hours; +/-8 minutes from hours 9 through 24) post-dose. If rescue occurs, scales/questions will be completed immediately each time rescue medication is taken ^d assessment will be completed immediately before first rescue medication is taken or at 24 hours post-dose

2.3 Determination of Sample Size

Assuming that the treatment difference between the combo and naproxen alone of 6.5 and common standard deviation of 16.9 with respect to SPID0-8, a total of approximately 528 subjects (144 subjects per active treatment arm and 48 in the caffeine and placebo using a 3:3:3:1:1 ratio) are required to

achieve 90% of power with the type I error of 0.05, a total of approximately 556 subjects will be randomized into the study if a drop-out rate of 5% is assumed.

2.4 Randomization

On Day 1, participants will be assigned a unique number (randomization number) in ascending numerical order at the study site. The randomization number encodes the participant's assignment to one of the five (5) arms of the study, according to the randomization schedule generated prior to the study by the Sponsor. Each participant will be dispensed blinded study intervention, labeled with his/her unique randomization number, throughout the study.

2.5 Blinding

Participants enrolled in the trial, investigators and their staff involved in protocol procedures or who are involved in data collection, data entry and data analysis will be blinded to the identity of the treatments until the database is locked. The study monitor will conduct product accountability after database lock. To preserve blinding, participants will be blindfolded during administration of study medication. Study drug will be dispensed by an unblinded study team member based on the randomization schedule. That team member may have no other role in the study conduct and may not reveal the study drug's identity to any members of the blinded study team.

3 DATA ANALYSIS CONSIDERATION

The statistical analyses will be performed by Quartesian Clinical Research (now a part of Veranex Solutions), using SAS Version 9.3 or higher. All Tables, Figures and Listings (TFLs) will be produced in landscape format. In general, all data will be listed by the Participant, treatment and visit/time point where as appropriate.

Data will be summarized by treatment group and visit/time. The total number of Participants in the treatment group (N) under the stated population will be displayed in the header of summary tables.

Data will be summarized using descriptive statistics for continuous variables. Unless otherwise stated, descriptive statistics will include total number of Participants (n), mean, standard deviation (SD), minimum, median, and maximum. In case n=0, except n, all other summary statistics will be kept blank and when n=1, only n, minimum and maximum will be reported, and all other summary statistics will be kept blank. The statistic "Missing" will also be evaluated by enumerating the number of missing entries/Participants, if any at that visit, and presented as a summary statistic only for the resulting time points.

In summary tables of categorical variables, counts and percentages will be used. The count [n] indicates the actual number of Participants with a particular value of a variable or event, which should always be less than or equal to the total number of Participants in the respective treatment group [N]. Percentage will be obtained by: % = (n/N) *100. Unless otherwise stated. Proportion will be obtained by: (n/N).

For ordinal-scaled variables, a combination of the above may be employed as appropriate: frequency and percentage of observations within a category and means and standard deviations of the scores of the categories. For categorical and ordinal variables, percentages will be calculated based on nonmissing data.

Decimal Precision Convention: The minimum and maximum statistics will be presented to the same number of decimal places as the original data. The mean and median will be presented to one more decimal place than the original data, whereas the standard deviation will be presented to two more decimal places than the original data. Also, the least square mean, standard error and its confidence interval, least square mean differences will be presented to two more decimal places than the original data. Also, the least square mean, standard error and its confidence interval, least square mean differences will be presented to two more decimal places than the original data. All percentages will be expressed to one decimal place. P-value will be presented three decimal places or P-value closer to zero will be presented as <0.001 and P-value closer to one will be presented as >0.999.

All dates will be displayed in DDMMMYYYY format.

3.1 Handling of Missing Data

3.1.1 Handling of Missing Data for Efficacy Assessments

Use of Rescue Medication:

In all analyses, for participants who take rescue medication, all pain intensity scores after intake of rescue medication will be imputed by the worse of the baseline or the score assessed immediately before taking rescue medication. All pain relief after intake of rescue medication will be imputed by "no relief" (0).

Missing data for efficacy parameter:

If Participants have missing pain data (i.e., pain intensity or pain relief scores) within the 24 hours period for the collection of pain rating data, but nonetheless complete the 24-hour period, then any missing timepoints will be replaced by a time-weighted average of the previous and the next available values (i.e., a linear interpolation for missing values) of the pain data (pain intensity / pain relief score). Intermittent missing data will only be imputed using linear interpolation method and if needed round down to the nearest whole number for pain relief scores, whereas for the categorical pain intensity the value will be rounded up to the nearest whole number.

Interpolation Formula,

$$y = \frac{y_2 - y_1}{x_2 - x_1} (x - x_1) + y_1$$

Where, and if needed round down to the nearest whole number for pain relief scores, whereas for the categorical paint intensity the value will be rounded up to the nearest whole number. y = missing pain data to be imputed, x = respective timepoint of y. y_1 and y_2 = pre and post available pain score of the missing pain data.

 x_1 and x_2 = respective timepoints of y_1 and y_2 .

If Participants do not complete the pain intensity/pain relief assessments for the full 24 hours, then the primary analysis will be calculated up to the last available timepoint, with no imputation for later timepoints.

In a sensitivity analysis, Participants who drop out of the study early because of a related AE or lack of efficacy will have later missing timepoints imputed using a worst-observation-carried-forward (WOCF) method, in which their worst observation at baseline or any time thereafter is imputed. For Participants dropping out early for any other reason, a last-observation-carried-forward (LOCF) imputation will be used.

No imputation will be done for missing data on stopwatch assessments of perceptible and meaningful pain relief. Instead, if data are missing for those assessments, data will be censored as described in Section 4.1.

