8.1.6 Postsurgery

During the post-surgery recovery period, participants will rest quietly, but will be encouraged not to fall asleep. Participants will be permitted to drink clear liquids following surgery. Participant may incorporate foods according to a soft diet following dosing beginning 60 minutes after dosing. Participants will not be allowed to eat 30 minutes prior to any planned assessments.

In order to qualify for randomization and continue in the trial, participants must have 'moderate' or 'severe' postoperative pain intensity on the Categorical Pain Rating Scale and a score of >5 on the NRS within 4.5 hours of the last suture.

Eligible participants will be assigned a participant randomization number and investigational products will be administered according to a generated randomization schedule (see Section 6.1.1).

Participants who have not met the randomization criteria within 4.5 hours from last suture or 14:30 h (+/- 15 minutes) will not be randomized and may be discharged from the clinic, once deemed eligible by an Investigator. Prior to being released from the clinic, discharge procedures will be reviewed with the participant. When discharged, all participants will need to make prior arrangements for travel and should not drive themselves home.

After the baseline (pre-dose) pain intensity is determined, pain intensity and pain relief will be rated by participants at 0.5, 1, 1.5, 2, 3, 4, 5, 6, 7, 8, 9, 10, 11, 12, 14, (16, 18, 20 if awake), 22 and 24 hours (+/-5 minutes over the first 8 hours; +/-8 minutes from hours 9 through 24) post-dose, and immediately prior to the use of the first dose rescue medication.

Instructions will be provided for use of the two stopwatches. A double-stopwatch method will be used to record time up to 24 hours after dosing for time to "first perceptible pain relief" (stopwatch A) and time to "meaningful pain relief *determined*" (stopwatch B). When the participant is administered study medication (following mouth inspection), the Study Coordinator or designee will start two stopwatches (one designated A and one designated B). The faces of the stopwatches will be covered so that the participant remains blinded to the exact time. To determine the time when the participant begins to perceive pain relief, the participant will be given stopwatch A after dosing and will be instructed to:

Page 38 of 67

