The durations between two time points will be calculated using the actual post-dose times of the pain score measurement. If the actual time is missing, then the nominal planned time will be used.

Pain Relief:

Participants will assess their current pain relief using a 5-point scale as 0: No relief, 1: A little relief, 2: Some Relief, 3: A Lot of Relief, 4: Complete relief (categorical scale). Each Participant will be instructed to mark the number indicating his or her current pain relief.

The Participant is to record pain relief (5-point categorical rating scale) at given time points during the 24-hour period and immediately before first use of rescue medication.

Total Pain Relief (TOTPAR):

Total pain relief (TOTPAR) is calculated by multiplying the pain relief score at each time point by the duration (in hours) since the preceding time point and then summing these over the relevant period.

$$TOTPAR_{0-2} = \sum_{i=1}^{4} (T_i - T_{i-1}) * PAR_i$$
$$TOTPAR_{0-4} = \sum_{i=1}^{6} (T_i - T_{i-1}) * PAR_i$$
$$TOTPAR_{0-6} = \sum_{i=1}^{8} (T_i - T_{i-1}) * PAR_i$$
$$TOTPAR_{0-8} = \sum_{i=1}^{10} (T_i - T_{i-1}) * PAR_i$$

Private and Confidential Study No 22093 Date: MAR 11, 2024

$$TOTPAR_{6-12} = \sum_{i=8}^{14} (T_i - T_{i-1}) * PAR_i$$
$$TOTPAR_{0-12} = \sum_{i=1}^{14} (T_i - T_{i-1}) * PAR_i$$
$$TOTPAR_{12-16} = \sum_{i=14}^{16} (T_i - T_{i-1}) * PAR_i$$
$$TOTPAR_{16-20} = \sum_{i=16}^{18} (T_i - T_{i-1}) * PAR_i$$
$$TOTPAR_{12-24} = \sum_{i=14}^{20} (T_i - T_{i-1}) * PAR_i$$
$$TOTPAR_{16-24} = \sum_{i=16}^{24} (T_i - T_{i-1}) * PAR_i$$

Where, $T_0=0$, T_i is actual post-dose time, PAR_i is the Pain Relief score at post-dose time T_i for all i > 0.

Peak Pain Relief:

Peak pain relief is the highest observed value of pain relief experienced during post-dose assessments of the study.

Peak Pain Intensity Difference (Peak PID):

Peak pain intensity difference is the highest observed value of pain intensity difference calculated by formula given above in this section.

Time to first Perceptible Relief:

Time to first perceptible relief is the time when the Participant experiences any perceptible pain relief after administration of study drug and stops the first stopwatch. If it is not stopped, time will be censored at the time of last pain relief score assessment or at the first use of rescue medication, whichever comes first.

Time to meaningful relief:

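### SAP 3.1.1 rounds interpolated relief scores down although TOTPAR needs no whole numbers, which can only lower the overnight TOTPAR windows, and it leaves the rounding of interpolated NRS scores undefined

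*SAP*

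**What the plan says.** SAP 3.1.1 covers participants who complete the 24 hours but have gaps: "any missing timepoints will be replaced by a time-weighted average of the previous and the next available values". Two rounding clauses follow, one for relief and one for intensity: "round down to the nearest whole number for pain relief scores, whereas for the categorical pain intensity the value will be rounded up". Both are repeated under the interpolation formula.

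The main source of gaps is planned. Protocol 8.1.6 schedules the late ratings at "14, (16, 18, 20 if awake), 22 and 24 hours", allows a six-hour overnight rest, and has participants woken for hour 22.

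The categorical intensity scale is headed "Categorical Pain Intensity Scale (predose)" in Protocol 10.5, and the schedule footnote in SAP 2.2 says it is "to be completed prior to dosing". The schedule also ticks Day 2 for it, but no post-dose time is defined. SAP 4.1 builds PID and SPID from the 0-10 NRS.

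SAP 4.1 obtains TOTPAR by "multiplying the pain relief score at each time point by the duration (in hours) since the preceding time point" and summing. After rescue, SAP 3.1.1 sets relief to 0.

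On whether interpolation reaches the main analysis, the SAP says two things. Section 7.7.2 and the summary table in 7.7.3 describe the ITT TOTPAR analysis as unimputed. Section 7.7.2 also says the endpoints are imputed under 3.1.1 when assessments are missing. Section 7.7.1 carries the same pair of statements for SPID0-8.

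**The concern.** Rounding in one direction only adds a one-sided error to a quantity that does not need rounding. TOTPAR and SPID are sums of score times hours, analysed by ANCOVA, and accept fractional scores.

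The error is not spread evenly. It falls on participants who are unrescued, asleep through the gap, and whose relief differs on either side of it. A participant rescued before hour 14 has relief 0 throughout the gap and nothing to round. An arm with fewer rescues therefore tends to lose more. Duration of analgesic efficacy is a stated secondary objective, and the late windows bear on it.

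The intensity clause is a separate defect. It names a scale with no post-dose values and is silent on the NRS. Two programmers following the SAP could round the NRS up or leave it unrounded, and would obtain different overnight SPIDs.

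**Working it through.** The documents give no figure for the effect of rounding, so there is none to reproduce. The sample size calculation concerns SPID0-8 and is not involved.

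**Inputs.** Flanking ratings at hours 14 and 22; missing hours 16, 18 and 20 (Protocol 8.1.6); relief scored 0 to 4; weight 2 h per rating (SAP 4.1); interpolation formula from SAP 3.1.1. Nominal times.

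**Formulae.** Interpolated relief at hour x is y = y14 + (y22 − y14)(x − 14)/8. Loss = sum of 2 h × (y − y rounded down). Rounding down never raises a value, so the loss is never negative.

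**All three hours missed.** Effect on TOTPAR12-24 and TOTPAR0-24:

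| Change, hours 14 to 22 | Example: values at 16, 18, 20 | Rounded down | Loss (point-hours) |
|---|---|---|---|
| 0 | 3, 3, 3 | 3, 3, 3 | 0 |
| 1 | 3.25, 3.5, 3.75 | 3, 3, 3 | 2 × 1.5 = 3.0 |
| 2 | 2.5, 3, 3.5 | 2, 3, 3 | 2 × 1.0 = 2.0 |
| 3 | 1.75, 2.5, 3.25 | 1, 2, 3 | 2 × 1.5 = 3.0 |
| 4 | 1, 2, 3 | 1, 2, 3 | 0 |

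Falling relief gives the same totals. Over a 12-hour window the TOTPAR12-24 maximum is 4 × 12 = 48, so 3.0 is 6.3% of the scale.

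**Hour 16 rated, hours 18 and 20 missed.** The gap is now 16 to 22. A one-category rise gives fractions 1/3 and 2/3, a loss of 2 × 1 = 2.0. A three-category change gives whole numbers at both hours and a loss of 0.

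**TOTPAR16-20.** For relief 3 at hour 14 and 4 at hour 22, a window holding only hours 18 and 20 falls from 2 × (3.5 + 3.75) = 14.5 to 12.0, of 16. The sum printed in SAP 4.1 runs from i = 16 to 18 and so also includes the interval ending at hour 16. It falls from 21.0 to 18.0, of 24.

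**Rescue before hour 14.** Relief is 0 on both sides of the gap; loss 0.

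**Sensitivity to clock time.** SAP 3.1.1 does not say whether the formula takes nominal or actual times; SAP 4.1 uses actual times for durations. If the hour-14 rating is 3 minutes late (14.05 h) and relief goes from 2 to 4, the value at hour 18 is 2 + 2 × 3.95/7.95 = 2.99. That rounds to 2 instead of 3 and costs nearly 2 point-hours. With actual times, the zero for a four-category change no longer holds.

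**Arm level (assumption).** Let f be the share of an arm that is unrescued, asleep at all three hours, and changed by one to three categories. The arm mean of TOTPAR12-24 is low by 2f to 3f: 0.2 to 0.3 at f = 0.1, 0.6 to 0.9 at f = 0.3, and 1.0 to 1.5 at f = 0.5. The difference between arms shifts by 2 to 3 times (f1 − f2), for example 0.4 to 0.6 at 0.3 against 0.1.

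**If the NRS were rounded up.** NRS 4 at hour 14 and 3 at hour 22 gives 3.75, 3.5, 3.25, all rounded to 4. Each PID is too low, and SPID12-24 loses 2 × (0.25 + 0.5 + 0.75) = 3.0.

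**The case against.** The strongest objection is that the rule may never reach the main TOTPAR analysis, because SAP 7.7.2 and 7.7.3 call the ITT analysis unimputed. That stands as a condition: the loss arises only where interpolation is used. It does not remove the point, because 7.7.2 also sends missing assessments to 3.1.1, and 3.1.1 interpolates for completers.

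Second, a six-hour rest ending at hour 22 would begin at hour 16, so many participants may have that rating. This stands. Missing all three hours is possible but is not the only reading, and the loss is smaller for one- and three-category changes when hour 16 is rated.

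Third, the effect on inference is small. Suppose, with nothing in the documents to support it, that 30% and 80% of two arms are rescued, every unrescued participant sleeps through the gap, and relief averages about 2.8 (SD 0.9, correlation 0.7). For hours 18 and 20, the simulated TOTPAR16-20 difference falls from about 5.5 to 5.1, or 8%. The expected z with 144 against 48 moves only from about 6.7 to 6.6, because rounding also reduces the variance. With 30% against 40% and 144 per arm, the difference falls from about 1.10 to 1.01 and z from 1.59 to 1.54. With equal rescue there is no systematic shift. About half of the sleepers in this model have unchanged relief and lose nothing. A reader might take the 8% as the size of the bias; the documents do not support that, because every input is assumed.

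Fourth, the rule is prespecified, conservative in intent, and keeps a 0-4 score on its scale. Prespecification is a merit, but the scale argument fails because the sums need no whole numbers. The per-time-point relief summaries are marked as unimputed, so they need no rounding either. Nor is it shown that plain interpolation is itself unbiased, since sleeping through a rating may relate to pain. The case for dropping the rounding is only that it removes an avoidable one-sided error.

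**Conclusion.** The point holds for secondary endpoints. Where interpolation is used, rounding down can only lower TOTPAR12-16, 16-20, 12-24, 16-24 and 0-24. For TOTPAR12-24 at nominal times the loss is 2.0 to 3.0 point-hours for an unrescued participant who misses all three overnight ratings and whose relief changes by one to three categories. It is 0 for unchanged relief and for anyone rescued before hour 14. A participant rescued between hours 14 and 22 may still have a rounded value before rescue. Late differences between arms shrink modestly when rescue rates differ; the amount depends on rescue and sleep rates that the documents do not give.

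Three stronger inferences are not supported. The primary result is not at risk: SPID0-8 and TOTPAR0-8 have no planned gap, the testing order covers SPID0-8 only, and the sample size does not change. The rule does not lower every interpolated value, only those that are not whole numbers. And naming the wrong intensity scale does not itself lower TOTPAR; its consequence is that rounding of the NRS in overnight SPID is undefined, and rounding it up would push SPID low.

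**What to change.** In SAP 3.1.1, delete both rounding clauses wherever they occur (in the paragraph on intermittent gaps and again under the formula). In their place, state that interpolated NRS intensity and relief values enter PID, SPID and TOTPAR unrounded. With the clauses gone, the reference to the categorical intensity scale goes too.

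In SAP 7.7.1 to 7.7.3, reconcile the two statements on imputation: say that interpolation of intermittent gaps is part of the ITT analysis, and that no imputation refers to time points after dropout. This fits 3.1.1, which interpolates for completers and leaves later time points unfilled for those who stop early.

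The cost is a few sentences of SAP wording. No new data are needed and the programming becomes simpler.
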